#### 5.3.3 Exploratory objectives

- To evaluate biochemical response (changes in CgA and NSE levels) and its association with response rate and progression-free survival.
- To assess whether baseline tumor and blood biomarkers may be predictive of response to lenvatinib.
- To explore additional hypotheses related to biomarkers and relationship to lenvatinib, neuroendocrine tumors, other endocrine disorders and/or cancer which may arise from internal or external research activities.

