4.3 Exploratory objective(s) and variables

The exploratory objectives are:

- To evaluate biochemical response (changes in CgA, 5-HIAA and NSE levels) and its association with response rate and progression-free survival.
- To assess whether baseline tumor and blood biomarkers may be predictive of response to lenvatinib.
- To explore additional hypotheses related to biomarkers and relationship to lenvatinib, neuroendocrine tumors, other endocrine disorders and/or cancer which may arise from internal or external research activities.

Exploratory variables:

- The changes in tumor markers (CgA, 5-HIIAA and NSE) will be analysed by cohort and significant reductions defined as 50% reduction or more regarding the baseline values will be calculated.
- The relationship between reductions and PFS and radiological response will be assessed.

EudraCT number: 2015-001467-39

Confidential Version 2.0

Page 10 of 16 Date: June 04, 2020

The second and third exploratory objectives will be assessed in the final analysis not in the interim analysis. According to the biomarkers that are available, the analysis of these objectives will be specified.

5. Study populations

The analysis sets will be defined as follows:

- Full Analysis Set will include all allocated subjects. This will be primary analysis set for the efficacy endpoints.
- Per Protocol Analysis Set will include those subjects who were allocated and received at least one dose of the assigned study drug and had no major protocol deviations. The subjects will complete both baseline and at least one post-baseline tumor assessments (week 6). Experior will send a list of major protocol deviations to establish the per-protocol set after the close out of data base. The PI ([name]) will decide which patients should be excluded to define the per protocol analysis set.
- Safety Analysis Set will include all subjects who were allocated and received at least one dose of the study drug and had at least one post-baseline safety evaluation (week 6). This will be the analysis set for all safety evaluations.

6. Statistical strategy

Below are detailed the statistical aspects of the data analysis.

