6.2.2 Statistical inference

Comparisons using log rank test or model of Cox proportional hazards multivariate analysis will be used if needed.

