6.3 Exploratory analysis

First secondary objective:

Significant reductions of tumor markers (CgA, 5-HIAA and NSE), defined as reductions of 50% or more regard the baseline values, will be showed by frequency tables.

To examine the relationship of biochemical response with PFS and radiological response the Kaplan-Meier and Chi-square/Fisher methods will be used.

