6.8 Statistical significance level

A significance level of 5% will be considered.

Page 15 of 16 Date: June 04, 2020

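### SAP 6.3 relates CgA, 5-HIAA and NSE change to response and PFS only through a yes/no 50% fall; an analysis on the continuous change should be added

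*SAP*

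**What the plan says.** The SAP's first exploratory objective (4.3) reads: "To evaluate biochemical response (changes in CgA, 5-HIAA and NSE levels) and its association with response rate and progression-free survival". Protocol 5.3.3 has the same objective with CgA and NSE only; the SAP adds 5-HIAA. Under exploratory variables, SAP 4.3 says "The changes in tumor markers (CgA, 5-HIIAA and NSE) will be analysed by cohort" without naming a method, defines a significant reduction as one of at least 50%, and adds: "The relationship between reductions and PFS and radiological response will be assessed".

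SAP 6.3 carries this out. The reductions, "defined as reductions of 50% or more regard the baseline values, will be showed by frequency tables", are then related to outcome: "To examine the relationship of biochemical response with PFS and radiological response the Kaplan-Meier and Chi-square/Fisher methods will be used".

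Regression is mentioned elsewhere, but not for the markers. SAP 6.2.2, under the secondary analysis, says: "Comparisons using log rank test or model of Cox proportional hazards multivariate analysis will be used if needed". Protocol 20.7 allows, optionally, multivariate regression for the primary endpoint and Cox models for PFS. SAP 6.9 lists assumption checks should a t test or a Cox model be applied. SAP 6.8 says "A significance level of 5% will be considered" and does not state sidedness.

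Protocol Table 5 schedules the markers at screening and at treatment visits with a tumor assessment. It limits 5-HIAA to patients of gastrointestinal origin, and its footnote makes NSE depend on local availability. SAP 6.11 uses available data without imputation.

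**The concern.** The objective speaks of changes in marker levels, which are continuous. Once cut at 50%, a 49% fall counts the same as a doubling, and a 51% fall the same as a 95% fall. Chi-square, Fisher and Kaplan-Meier by group then see only the yes/no variable. An analyst who follows 6.3 as written produces no graded estimate of association, such as an odds ratio or hazard ratio per halving of the marker.

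The cohorts are small. At the design ORR of 25%, 55 patients give 55 × 0.25 = 13.75, so about 14 responders. At 10% there would be 5 or 6. What is at stake is the efficiency and readability of an exploratory result, in a phase II study meant to indicate whether the markers are worth following up.

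**Working it through.** **Inputs from the documents.** 55 patients per cohort, ORR 25% against 10%, 90% power and a 5% level (Protocol 20.6); the 50% cut and the grouped methods (SAP 6.3). **Assumed, because the documents are silent:** a two-sided 5% test, a normally distributed (log) marker change, the strength of the relation, the share reaching the cut, and the number of PFS events.

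**Step 1: the plan's own figure.** In an exact single-stage binomial design with one-sided 5%, the smallest n is 55, declaring success at 10 or more responses: P(X ≥ 10 | 0.10) = 0.0444 and P(X ≥ 10 | 0.25) = 0.911. So 55 reproduces. It was sized for ORR; no power is stated for the marker analysis.

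**Step 2: why a cut loses information.** For a normal variable with a small linear effect, a split with share p above the cut keeps a fraction φ(z)²/[p(1−p)] of the information, where z is the upper p point. At p = 0.30, z = 0.524 and φ = 0.348, so 0.348²/(0.3 × 0.7) = 0.58. At p = 0.15 it is 0.43, and at p = 0.45 it is 0.63.

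**Step 3: response, worked case.** Take 14 responders and 41 non-responders, a mean difference of 0.8 SD, and 30% reaching the cut.
- Continuous: 0.8 × √(14 × 41/55) = 2.58; power ≈ Φ(2.58 − 1.96) = 0.73.
- Cut: it lies 0.75 SD above the non-responder mean, so 52.0% of responders and 22.7% of non-responders reach it, a difference of 0.293. The SE is 0.142 under the null and 0.149 under the alternative. Power of the uncorrected Chi-square ≈ Φ[(0.293 − 1.96 × 0.142)/0.149] = 0.54.

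Repeated simulations of this case gave 68% to 71% for Wilcoxon, 55% to 59% for Chi-square and 47% to 49% for Fisher. The cut therefore costs about 12 to 13 points with Chi-square and 21 to 22 with Fisher.

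**Step 4: ranges under a smooth relation, n = 55.**

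| Outcome | Assumptions | Power lost by the cut |
|---|---|---|
| Response | 0.6–1.0 SD; 15–45% reach the cut; ORR 25%; Wilcoxon | 8–19 (Chi-square), 17–28 (Fisher) |
| Response | 0.5–1.2 SD; 20–50% reach the cut; ORR 25% or 40%; t test | 7–25 (Chi-square), 10–33 (Fisher) |
| PFS | HR 0.8 to 0.5 per SD; 20–50% reach the cut; 70% or 90% events | 7–42 (log-rank vs Cox) |
| PFS | HR 1.42–1.73 per SD; 15–45% reach the cut; about 42 events | 18–49 (log-rank vs Cox) |

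Two PFS cases, each with 30% reaching the cut: at HR 0.7 per SD and 70% events, 57% (Cox) against 30% (log-rank); at HR 1.57 per SD and about 42 events, 79% against 48%. With PFS counted from week 6 and earlier events dropped, the gain from the continuous analysis was still about 17 to 51 points.

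**Step 5: where the loss vanishes or reverses.**
- Weak or very strong effects (0.2 to 0.3 SD, or 1.5 to 2.0 SD; ORR 25%; 30% reach the cut): the loss is 0 to 3 points against Chi-square and 0.5 to 6 against Fisher. For example, at 0.3 SD power is 14.6% (Wilcoxon), 13.7% (Chi-square) and 9.1% (Fisher).
- True step at the cut: the cut wins by 1 to 28 points for response (Chi-square vs Wilcoxon) and about 3 to 23 for PFS. For example, if 30% reach the cut and 50% of them respond against 14.3% of the rest, Chi-square has 80.2% and Wilcoxon 60.3%.

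**Step 6: type I error.** With no effect (30% reaching the cut), rejection was 4.9% for Wilcoxon, 5.0% for Chi-square and 3.2% for Fisher. The gain of the continuous test is not bought with false positives.

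**Step 7: fewer patients.** At n = 40, with 70% events and a smooth relation, the PFS loss was 6 to 44 points.

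**The case against.** Four points on the other side carry weight.

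- *A responder definition is a legitimate way to read biochemical response.* Agreed. Fixing a 50% cut in advance is better than choosing one after seeing the data, and citing no guideline for it is not an error. The gap is only that nothing stands beside it.
- *The SAP does not discard the continuous data.* Also agreed. SAP 4.3 plans an analysis of the changes by cohort, and Protocol 20.7 and SAP 6.2.2 and 6.9 leave room for regression. But all of this is optional or without a method, and none of it names a marker-outcome model. The accurate description is that a continuous analysis of association is not specified.
- *The power figures rest on assumptions the plan does not supply.* A reader might infer that the plan forfeits a fixed 10 to 30 points. The documents do not support that: they give no effect size, marker SD or share reaching 50%, and Step 5 shows that the loss can be zero or change sign. For PFS, Kaplan-Meier is not a test, so the log-rank comparison measures something that 6.3 does not name.
- *A week-6 marker value changes more than the scale.* The SAP states no time point for the 50% fall, so fixing week 6 also settles when change is measured, and it drops patients who progress, die or lack a value by then. This is a real cost. The PFS gain nevertheless persisted when early events were dropped.

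**Conclusion.** The point holds as an optional improvement in efficiency. SAP 6.3 examines association only through the 50% cut. Under a smooth relation of moderate strength, with at most 55 patients per cohort, ORR 25% and 15% to 45% reaching the cut, that costs roughly 7 to 33 points of power for response, and roughly 7 to 50 for PFS if a log-rank test is used. Very weak or very strong effects bring the loss close to zero, and a true step at 50% favours the cut.

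Fifty-five is a ceiling: 5-HIAA is measured in one cohort, NSE depends on the site, and missing values are not imputed.

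A reader might also infer that a real association would probably be reported as absent. That does not follow: in the worked case the cut still has 47% to 59% power, about an even chance of detection. The objective is exploratory and has no power target or decision rule. The primary ORR result and the secondary endpoints are unaffected.

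**What to change.** In SAP 6.3, keep the 50% frequency tables, the Chi-square/Fisher comparison and the Kaplan-Meier curves. They remain the better analysis if the effect is a true step. Add, for each marker and cohort, an analysis of log(on-treatment value / baseline) at the week-6 tumor-assessment visit (Cycle 2 Day 15 in Protocol Table 4):

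- response: a Wilcoxon test of responders against non-responders, and logistic regression giving the odds ratio per halving of the marker with 95% CI;
- PFS counted from that visit: a Cox model giving the hazard ratio per halving with 95% CI;
- the number of patients with evaluable values for each marker and cohort.

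The cost is one SAP paragraph and a few lines of R, with no new data, visits or patients. The downsides are a log-linear assumption behind the odds and hazard ratios, and the loss of patients who progress, die or lack a marker value by week 6.

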6.4 Subgroup analysis

Subgroup analysis for ORR, PFS, OS, biochemical response (tumor markers) will be performed outside the indications of the study protocol. The following variables will be part of this analysis to explore differences between subgroups of subjects:

ORR:

- Origin of gastrointestinal NET.
- Functionality.
- Tumor burden (this information will be extract from central radiologic assessment).
- Number of previous lines (1, 2 or 3 lines) (only in pancreatic NET cohort).
- Concomitant use of somatostatin analogues.
- Previous treatment with everolimus or sunitinib (only in pancreatic NET cohort).

PFS:

- Origin of gastrointestinal NET.
- Tumor burden.
- Number of previous lines (1, 2 or 3 lines) (only in pancreatic NET cohort).
- Concomitant use of somatostatin analogues.

Page 12 of 16

Date: June 04, 2020

- Page 13 of 16 Date: June 04, 2020
- Previous treatment with everolimus or sunitinib (only in pancreatic NET cohort).
- o ECOG.
- Prior surgery.
- Age (≤ 65 vs > 65 years).
- o Differentiation grade (G1/G2).
- Radiological response (upon central radiologic assessment).
- OS:
 - Functionality.
 - o Tumor burden.
 - Concomitant use of somatostatin analogues.

Survival curves will be calculated for OS

In addition to the subgroup analysis, it will be calculated:

- Duration of response will be assessed and represented graphically. It will be calculated as time since treatment initiation to progression disease.
- Time to follow-up will be described.

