Calendar and estimated completion dates	Recruitment Start: September 2015 End of Recruitment Period: March 2017 3rd Tumor assessment of LP (Primary Analysis): July 2017 Database Lock for Interim Analysis: October 2017 End of Follow up Period: March 2019 FPFV: September 2015 LPLV: September 2018 Clinical Study Report: September 2019		

2. Tab	ole of contents	
1. Sy	nopsis	3
2. Tal	ble of contents	6
3. Ab	breviations	7
4. Stu	ıdy objectives and variables	8
4.1	Primary objective(s) and primary variable(s)	
4.2	Secondary objective(s) and secondary variables	
	secondary objective(s) and secondary variables	
4.3	Exploratory objective(s) and variables	
The e	exploratory objectives are:	
	pratory variables:	
	idy populations	
	itistical strategy	
6.1		
6.1.1	Primary analysisSummary statistics	
6.1.2	Statistical inference	
6.2	Secondary analysis	
	econdary analysis will be based on the Full Analysis Set and the Safety Ana	
Set		
6.2.1	Summary statistics	11
6.2.2	Statistical inference	12
6.3	Exploratory analysis	12
6.4	Subgroup analysis	12
6.5	Safety analysis	13
6.5.1	Summary statistics	
6.5.2	Statistical inference	
6.6	Demographic and baseline characteristics	
6.7	Concomitant medications	
6.8	Statistical significance level	
6.9	Statistical model assumptions	
6.10	Transformation of expected variables	
6.11	Handling of missing data	
6.12	Description of the softwares to be used for data analysis	
6.13	Interim analysis protocol	
7. Ref	ferences	16

Confidential Version 2.0

GETNE
TALENT Statistical Analysis Plan

Page 7 of 16 Date: June 04, 2020

3. Abbreviations

AE:

Adverse Event

CgA:

Chromogranin A

CR:

Complete Response

DpR:

Deepness of Response

ECG:

Electrocardiogram

eCRF:

electronic Case Report Form

ETS:

Early Tumor Shrinkage

G1:

Grade 1

G2:

Grade 2

GETNE:

Grupo Español de Tumores Neuroendrocrinos

HPMC:

Hydroxypropyl Methylcellulose

NSE:

Neuron Specific Enolase

OOR:

Objective Response Rate

OS:

Overall Survival

PFS:

Progression-Free Survival

PI:

Principal Investigator

PR:

Partial Response

RECIST:

Response Evaluation Criteria In Solid Tumors

SAE:

Serious Adverse Event

WHO:

World Health Organization

4. Study objectives and variables

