6.10 Transformation of expected variables

• The ORR is defined as the proportion of subjects who have best overall response of CR or PR (by RECIST 1.1):

- The time to progression is defined as the difference between start of drug (C1D1) and the progression date or death (whichever occurs first) or the last tumor assessment documented.
- ETS rate is defined as 20% reduction in target lesions after the first 6 weeks of treatment.
- DpR is defined as percentage of maximum tumor shrinkage observed at the nadir (the minimum of total sum of diameters) compared with baseline.
- Overall survival is defined as the time from the start of drug (C1D1) to death.

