6.13 Interim analysis protocol

The interim analysis will be performed when the last patient included in the corresponding cohort of the study will have at least two tumor assessments (12 weeks after the last patient recruited).

Page 16 of 16 Date: June 04, 2020

7. References

- 1. Guidance for Industry: Clinical Trail Endpoints the Approval of Cancer Drugs and Biologics (May 2007).
- 2. R Core Team (2015). R: A language and environment for statistical computing. R Foundation for Statistical Computing, Vienna, Austria. URL (http://www.R-project.org/).

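### SAP 6.4 counts duration of response from treatment start, and PFS is compared by on-study response with no landmark or time-dependent method

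*SAP*

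**What the plan says.** **Duration of response.** SAP 6.4, after the subgroup lists, adds a duration of response that will be assessed and plotted: "It will be calculated as time since treatment initiation to progression disease". It names no responder population, no rule for death and no censoring rule. SAP 6.10 uses the same origin for another quantity: "The time to progression is defined as the difference between start of drug (C1D1) and the progression date or death", or else the last documented tumor assessment. The protocol does not define duration of response, so nothing there corrects the SAP.

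**PFS by response.** The PFS subgroup list in SAP 6.4 sets one post-treatment variable beside baseline factors such as age and grade: "Radiological response (upon central radiologic assessment". For tumor markers, SAP 6.3 says: "To examine the relationship of biochemical response with PFS and radiological response the Kaplan-Meier and Chi-square/Fisher methods will be used". SAP 4.3 defines the marker response without a visit or window: "significant reductions defined as 50% reduction or more regarding the baseline values will be calculated". Protocol Table 5 repeats the markers at visits with a tumor assessment (NSE where a site can measure it). The only time-to-event comparisons named are log-rank or Cox, if needed (SAP 6.2.2; protocol 20.7).

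**Timing.** SAP 4.3 states: "The second and third exploratory objectives will be assessed in the final analysis not in the interim analysis". The marker-PFS objective is the first, so it is not deferred. SAP 6.13 sets the interim when the last patient in the cohort "will have at least two tumor assessments (12 weeks after the last patient recruited".

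**The concern.** Two different time origins are being mixed.

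A duration of response should begin when the response is first documented. Counted from C1D1, it is PFS-type time under another name. In a single-treatment trial with ORR as the primary endpoint, durability is read beside the response rate, so an inflated figure would make responses look more lasting than they are.

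The PFS contrasts have the related problem of guarantee time. A response can be recorded only in a patient who is still progression-free at that scan. Grouping patients from C1D1 by a response seen later gives responders a stretch of follow-up in which they could not have progressed. Response, or a marker fall, could then appear to predict longer PFS when it does not. For the marker this arises only if a later visit can supply the fall, and the SAP does not exclude that.

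**Working it through.** **1. The plan's own figure.** The SAP gives no number for this point. The one computed design figure, 55 per cohort (protocol 20.6), reproduces with an exact one-sided single-stage test: at least 10 of 55 responses gives alpha 0.0444 and power 0.911 for 10% versus 25%. It is used below only as the cohort size.

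**2. Duration of response.** For a responder,

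(progression date − C1D1) = (progression date − response date) + (response date − C1D1).

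The SAP's quantity is the left side, so it exceeds the true duration by the time to response. Protocol 12.2 schedules scans at weeks 6 and 12, then every 12 weeks. With a month of 30.4375 days:

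- week 6: 42 / 30.4375 = 1.4 months
- week 12: 84 / 30.4375 = 2.8 months
- week 24: 168 / 30.4375 = 5.5 months

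The excess is smaller if an earlier unscheduled scan shows the response.

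**3. Assumptions for the PFS contrasts.** None of these is in the documents:

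- Exponential PFS with median 6, 12 or 18 months.
- Potential first response at weeks 6/12/24/36/48 with weights early 50/30/20%, middle 25/35/25/15%, late 10/25/30/20/15%.
- Response counts only if it precedes progression, and has no effect on the hazard.

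Observed ORR is set to 25% or 10%, the protocol 20.6 values. Follow-up comes from the SAP calendar: recruitment September 2015 to March 2017 and "FPFV: September 2015 LPLV: September 2018" give 18 to 36 months. The March 2019 end of follow-up gives 24 to 42. At the interim, 12 weeks after the last patient plus 18 months of recruitment gives 2.8 to 20.8 months.

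**4. Duration medians.** Under exponential PFS the true median duration from response equals the median PFS. Counted from C1D1 (early/middle/late), it becomes 8.5/9.6/11.2 months at a true 6.0, 14.5/15.8/17.5 at 12.0 and 20.6/21.8/23.7 at 18.0.

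**5. Spurious hazard ratios.** Responders versus non-responders from C1D1, ORR 25%, 18 to 36 months; true value 1.00:

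| Median PFS (months) | Early | Middle | Late | Rejection by a 5% log-rank test, n = 55 |
|---|---|---|---|---|
| 6 | 0.70 | 0.61 | 0.50 | 17/32/59% |
| 12 | 0.79 | 0.71 | 0.61 | 8/12/24% |
| 18 | 0.82 | 0.75 | 0.65 | 6/9/15% |

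- Follow-up 24 to 42 months, median 12: 0.81/0.73/0.64. Complete follow-up: 0.83/0.77/0.69.
- ORR 10%, 18 to 36 months: 0.58 to 0.85; rejection 4 to 15%.
- Dating progression at the scan moves the 18 to 36 month values by at most 0.02.
- Marker at the interim, median 12, fall counted at any visit: 0.67/0.58/0.48 when about 21 to 24% of patients show a fall by that cut, and 0.61/0.51/0.41 when about 34 to 39% do.

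**6. Other assumptions.** With a constant chance of first response at each scan to week 48 and a fixed 104 weeks of follow-up, the median hazard ratio at ORR 25% was 0.60 to 0.66 for median PFS of 9 to 18 months. The log-rank test rejected in 29% down to 13% of trials. A week-24 landmark brought this to 5.5 to 5.7%.

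**7. Does the remedy work?** At 18 to 36 months and ORR 25%, a time-dependent Cox model gives 1.00 to 1.01 with 5 to 6% rejection. A week-12 landmark gives 0.99 to 1.00 with 5 to 8%. For a marker fixed at week 6 with a 40% fall, comparing only sampled patients gives 1.00; counting unsampled patients as non-responders gives 0.78/0.85/0.88 at median 6/12/18.

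**The case against.** The strongest reply is about weight.

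- **Status.** Duration of response is not an objective or variable in SAP 4.1 to 4.3. It and PFS by radiological response sit in a section that the SAP itself places outside the protocol, and the marker analysis is exploratory. No decision rule depends on any of them. This stands, and it limits the weight of the PFS contrasts. It does not make the duration definition right: that output is planned and would be reported under a name it does not fit.
- **Silence is not error.** The SAP does not say how patients are classified for the PFS contrasts, and a Cox model can carry response as a time-dependent covariate. This is fair. The bias follows if ever-response is used as a fixed group from C1D1; the defect is that no method is stated to prevent that. Kaplan-Meier by marker response, the one method SAP 6.3 names for PFS, leads there unless a visit is fixed.
- **Invented inputs.** Median PFS, response timing and marker-fall share are assumed, and the log-rank test is allowed but not assigned to these contrasts. The rejection rates run from 4% to 59%, so they illustrate a mechanism rather than size it for this trial. This stands.
- **Follow-up.** The SAP is dated June 2020, so the real cut may be later. With 39 to 57 months (March 2017 and September 2015 to June 2020) the median-12 values become 0.82/0.75/0.67: smaller, but the bias remains.
- **Interim.** Running the marker-PFS contrast at the interim is an inference from what SAP 4.3 leaves undeferred. Nothing schedules it there explicitly.

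**Conclusion.** Both parts hold. The duration of response in SAP 6.4 is wrong as written: it overstates each responder's duration by the whole time to response, and this needs no modelling assumption. It should be corrected before durability is reported.

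The PFS-by-response analyses lack any protection against guarantee-time bias. Used with ever-response as a fixed group, they favour responders whatever the assumed timings; how strongly depends on PFS, response timing and follow-up that the documents do not give. Shorter follow-up makes it worse, so an interim reading of the marker contrast would be the most affected. The hazard ratio stays biased at ORR 10%, although a test there may reject less often than its nominal 5%. Taken alone, this part is of lower weight.

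ORR, the sample size, ETS, DpR and overall PFS are not affected.

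**What to change.** - **Duration of response:** define it in responders only, from the date of the first centrally read CR or PR to progression or death, with the censoring rules of SAP Table A.
- **PFS by radiological or marker response:** use response as a time-dependent covariate, or a pre-stated landmark such as week 12, and label the result descriptive.
- **Marker response:** state the visit at which the 50% fall is judged, and whether the contrast is run at the interim, the final analysis or both. If it is fixed at week 6 and PFS is compared only among patients sampled then, no further correction is needed.

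The cost is SAP wording and minor programming on dates already collected. Precision will be poor either way: 55 × 0.25 is about 14 responders per cohort, and 55 × 0.10 is 5 or 6. A week-12 landmark drops patients who progress earlier: with exponential PFS, 55 × (1 − 0.5^(2.8/median)) is about 15, 8 or 6 at median 6, 12 or 18 months. It also counts later responders as non-responders (14 to 60% of responders under the assumed timings). About 5 to 11 landmark responders per cohort remain at ORR 25%, and 2 to 4 at ORR 10%. With so few, a landmark test is itself unreliable: the week-24 version rejected in 7 to 10% of trials at ORR 10%. That is a further reason to report these contrasts descriptively.
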